## List of Abbreviations and Definitions

[  F]FEMPA	N-{2-[2-[  F]fluoroethoxy]-5-methoxybenzyl}-N-[2-(4-methoxyphenoxy)pyridine-3-yl]acetamide
Beta-HCG	Beta-human chorionic gonadotropin
CI	Confidence Interval
CRF	Case Report Form
CSF	Cerebrospinal fluid
CSOC	Clinical Study Oversight Committee
DNA	Deoxyribonucleic acid
DTI	Diffusion tensor imaging
ECAS	Edinburgh Cognitive and Behavioural ALS Screen
ECG	Electrocardiogram
eCRF	Electronic Case Report Form
EDC	Electronic data capture
FVC	Forced Vital Capacity
GCP	Good Clinical Practice
HIPAA	Health Insurance Portability and Accountability Act
HREC	Human Research Ethics Committee

**List of Abbreviations and Definitions (continued)**

ICH	International Conference on Harmonization
IUD	Intrauterine device
MBq	Megabecquerels
MRI	Magnetic Resonance Imaging
MGH	Massachusetts General Hospital
NOAC	Novel oral anticoagulants
PET	Positron Emission Tomography
PT	Preferred Term
QA	Quality Assurance
QC	Quality Control
SAE	Serious Adverse Event
ST	Symptomatic Therapy
TSP0	Translocator Protein
ULN	Upper Limit of Normal
UMN	Upper Motor Neuron
UMNS	Upper Motor Scale

## 3K3A-APC in ALS Protocol Synopsis

Protocol Number	ZZ-3K3A-202
Protocol Title	A Phase 2 Open Label Trial of 3K3A-APC in Amyotrophic Lateral Sclerosis
Sponsor	Macquarie University
Investigator	[name]
Study Centre	Macquarie University
Study Period	3 months
Study Objective and Specific Aims	
The primary objective of this study is to determine the safety and potential effective dose of a novel therapy, 3K3A-APC in a small cohort (n=16) of patients with Amyotrophic Lateral Sclerosis (ALS).
 
The specific aims to accomplish the primary objective are:
 
 
To recruit patients with ALS according to established diagnostic criteria with Upper Motor Neuron features.
 
To administer in a hospital environment two dose levels of a novel therapy, 3K3A-APC, to patients with ALS monitoring for safety.
 
To investigate the biological effect of 3K3A-APC in the cohort employing a range of biometric, imaging and biological methods.
 
To use the data from this pilot study to inform a larger study to assess the effectiveness of 3K3A-APC as a potential therapy to slow the progression of ALS.
 

Study Design	Cross sectional, single centre study to assess safety of 3K3A-APC in a small cohort of patients with clinically definite ALS, incorporating a range of imaging and biologic markers to determine the biological impact of the therapy.
Number of Subjects	
16 Subjects Enrolled
 
 
○ Clinically Definite ALS according to Awaji Criteria
 
○ Established Upper and Lower Motor involvement
 

Main Eligibility Criteria	
Amyotrophic Lateral Sclerosis (ALS) Subjects:
 
Inclusion:
 
 
• Patients must have clinically definite ALS (Awaji Criteria)
 
• Male or female age 18 years and less than 75 years at time of ALS study.
 
• Symptom onset less than 38 months before screening.       
 
○ Participants who fail to meet this criterion may be considered at the Principal Investigator's discretion, provided the participant is clinically stable and without any safety concerns.
 
 
 
• Diagnosis of ALS less than 26 months before screening.       
 
○ Participants who fail to meet this criterion may be considered at the Principal Investigator's discretion, provided the participant is clinically stable and without any safety concerns.
 
 
 
• Clinically definite Upper Motor Neuron signs
 
 
Exclusion:
 
 
• Current treatment with anticoagulants (e.g., warfarin, novel oral anticoagulants, heparin) that might preclude safe completion of the lumbar puncture.
 
• Condition that precludes the safe performance of routine lumbar puncture, such as prohibitive lumbar spinal disease, bleeding diathesis, or clinically significant coagulopathy or thrombocytopenia.
 
• Use of investigational drugs or devices within 60 days prior to Baseline (dietary supplements taken outside of a clinical trial are not exclusionary, e.g., coenzyme Q10).
 
• Prolonged prothrombin time or activated partial thromboplastin time >2xULN
 
• Severe hypertension or hypotension
 
• Glomerular filtration rate (GFR) <35 mL/min
 
• Forced vital capacity (FVC) at screening of <50% of predicted.       
 
○ Participants who fail to meet this criterion due to technical difficulties may be considered at the Principal Investigator's discretion.
 
 
 
• Prior exposure to any exogenous form of APC
 
• Inability to lie flat for procedures (MRI, PET, LP).
 

----------------------------------	---

	
 
• Pregnant or lactating during the study period
 

Primary Outcome	
The primary study outcomes are:
 
To ensure the safety of patients with ALS administered a range of doses of 3K3A-APC according to a fixed dose regimen of five doses of 15mg or 30mg doses given 12 hours apart.
 
This study also aims to determine whether a novel therapy, 3K3A-APC, is able to attenuate microglial activation in the motor cortex of patients with amyotrophic lateral sclerosis utilizing serial [F]FEMPA PET imaging (Day 2 and Day 9). In addition, the study design will include two (2) dose cohorts with eight patients in each cohort, with the initial cohort to receive 15mg and the subsequent cohort to receive 30mg, to determine the dose of 3K3A-APC that is shown to be most effective in reducing microglial activation. If microglial activation can be attenuated in ALS, then the progression of ALS might be slowed.

Secondary Outcomes	
The secondary outcomes are:
 
 
• Comparison between the changes in the mean of clinical, imaging and biomic outcomes in various subsets between the two dose cohorts.
 
• The secondary outcome instruments to be employed are: 
 
• MRI scan of the brain (Day 2 and Day 9), to determine whether the blood brain barrier integrity can be measured in ALS by Magnetic Resonance Imaging, and whether 3K3A-APC is able to repair it.
 
• Biomic measurements of serum, plasma, urine and CSF. This includes a novel method to determine whether monocyte activation in the peripheral blood can act as a surrogate marker of microglial activation state in ALS.
 
• These methods will determine whether 3K3A-APC therapy is able to attenuate the altered cytokine and metabolic profiles in ALS.
 
 
 

Safety Assessments	
Incidence of adverse events, proportion of withdrawals due to adverse events, vital signs and clinical laboratory assessment changes from baseline. Clinical safety laboratory data (haematology, biochemistry, and urine chemistry) will be summarised at each protocol scheduled time point, by

	dose cohort, and overall. Observed values, change from baseline will be presented.
Statistical Methods	
Descriptive analyses will be reported for this study. Continuous parameters, will be summarised as the number of observations, mean, median, standard deviation, minimum, maximum, and if appropriate two-sided 95% CI's. Categorical parameters will be summarised as frequencies, percentages, and exact Clopper-Pearson two-sided 95% CI's. Data will be summarised by dose cohort, and overall.
 
Primary efficacy variables:
 
Adverse events will be coded using the most recent version of the Medical Dictionary for Regulatory Activities (MedDRA) coding system to give a System Organ Class (SOC) and Preferred Term (PT) for each adverse event (AE).
 
Treatment emergent AEs will be defined as AEs with an onset date on or after the date of administration of study drug. If the onset date is missing, the AE will be considered to be treatment emergent. Only treatment-emergent AEs will be summarized. All reported AEs will be listed. The number of AEs, and the number and percentage of patients reporting at least one AE will be summarized by PT nested within SOC for required AE types. AE data will be summarized by dose cohort, and overall.
 
Microglial activation will be summarised at each time point for each dose cohort and overall as observed value, change from baseline, and % change from baseline. Microglial activation will be summarised with number of observations, mean, median, standard deviation, minimum, maximum, and two-sided 95% CI's.
 
Secondary efficacy variables:
 
The secondary efficacy variables of MRI scan of the brain, and biomic measurements of serum, plasma, urine and CSF will be summarized over time for each dose cohort, and overall as for the primary efficacy variables.

Data Access	Data will be password protected and securely stored at Macquarie University and with the contract data management team. All personally identifiable information will be removed before it is shared outside the study.

### Schedule of Activities – ALS Subjects

Visit Number	SC	V1	V2	V3	V4	V5	V6	V7	V8	V9	V10	V11
Day of the Week		M	T	W	T	F	S	S	M	T	W	M
Visit Description (Day)	-30	1	2	3	4	5	6	7	8	9	10	15
Written Informed Consent	X											
Inclusion/Exclusion Criteria	X	X										
Vital Signs	X	X	X	X	X	X	X	X	X	X	X	X
Physical Examination	X	X							X			X
Neurological Examination	X	X							X			X
ECAS	X											
FVC	X											
ECG	X	X	X	X	X	X			X	X	X	X
Pregnancy Test (Urine)	X	X							X			
Blood Sample for TSPO genotype	X											
Clinical Laboratory Assessments	X a	X	X	X a	X a	X a	X	X	X	X	X a	X a
Research blood and urine samples	X	X	X	X	X	X			X	X	X	X
Lumbar Puncture for CSF examination				X							X	

Visit Number	SC	V1	V2	V3	V4	V5	V6	V7	V8	V9	V10	V11
Day of the Week		M	T	W	T	F	S	S	M	T	W	M
Visit Description (Day)	-30	1	2	3	4	5	6	7	8	9	10	15
MRI (ALS Protocol)			X							X		
PET imaging ([  F]FEMPA)			X							X		
Administration of 3K3A-APC - 5 doses (every 12 hours)				X	X	X						

a – Urine collected for urinalysis

Confidential

## 1. Introduction and Rationale for this Study

Multiple mechanisms are suggested to be involved in the cause of sporadic ALS, with evidence for many pathogenic processes, none of which clearly lead to significant therapies. These include excitotoxicity, oxidative stress, impaired cellular defence mechanisms and immune-mediated inflammation, to name just a few. There is considerable evidence that inflammation is central in the pathogenesis of ALS. Microglia are critical in this inflammatory response, both as detectors of motor neuronal injury and in the effector response that ultimately produces motor neurone death and progression of disease. The earliest change that occurs in the pathology of ALS is activation of microglia, both in post-mortem human ALS tissue and in animal models of ALS. Activated microglia and astrocytes are found in close proximity to dying motor neurons. Their activation status and proliferation seemingly increases with disease progression.

Inflammatory microglia and monocytes have been considered as a therapeutic target in ALS, but to date only a few trials exist where attenuation of microglial activation is the principal mechanism of action (1).

It is now possible to measure *in vivo* activated microglia in the CNS utilizing a PET imaging technique targeting the microglial 18kD translocator protein, TSPO. In a small trial of 10 patients, Zurcher et al were able to show that [C]-PBR28 positron emission tomography revealed increased binding in the motor cortices and corticospinal tracts in patients with ALS compared to healthy controls (2). This technique may therefore be utilized to measure end organ effectiveness of a therapeutic intervention to downregulate microglial activation, and has been replicated in further studies, including therapeutic studies in other diseases (3). We now have access to an F ligand for TSPO termed FEMPA (Piramal) at Macquarie University in collaboration with Cyclotek and Piramal (4).

APC is an endogenous serine protease with systemic anticoagulant, anti-inflammatory, and anti-apoptotic activities. 3K3A-APC is a 405-residue protein expressed via recombinant technology in Chinese hamster ovary (CHO) cells. Its amino acid sequence differs from that of the wild-type human Activated Protein C (APC) and of the product drotrecogin alfa (activated) (Xigris®) in that 3 sequential lysine residues have been replaced with 3 sequential amino-acid substitutions (all lysine to alanine); the amino acid substitutions are K191A-K192A-K193A. This change retains the cytoprotective effects of native (wild-type) APC while significantly reducing its anticoagulant effects. 3K3A-APC is an APC variant that has been genetically engineered to maximize neuro- and cytoprotective activity and minimize anticoagulant activity. 3K3A-APC is currently in development for the treatment of moderate to severe acute ischemic stroke (ZZ Biotech – see investigational brochure). A Phase 1 trial of 3K3A-APC was completed in healthy volunteers (NCT01660230), with demonstrated safety. Intravenous administration of 3K3A-APC in multiple dose levels did not result in any serious adverse events, severe adverse events or withdrawal from study due to an adverse event (5). A Phase 2 trial of 3K3A-APC in Ischemic Stroke

(NCT02222714) has also finished (6). The doses of 3K3A-APC being evaluated in the study were 120, 240, 360 and 540 µg/kg. These doses were based on the doses and administration that were tested in the Phase 1 clinical study in normal human volunteers during which single- and multiple-dose (q12 hours for 5 doses) infusions were well tolerated at doses up to 540 µg/kg. Further study has demonstrated no relationship between clearance and body weight, so further ongoing trials with 3K3A-APC now utilize fixed doses to achieve the same blood levels of the investigational product.

3K3A-APC's cytoprotective activities are mediated by proteolytic activation of protease activated receptor 1. In addition, it has been shown that 3K3A-APC has powerful anti-inflammatory action, with reduction of microglial numbers and activation state. In 2009, Zhong et al demonstrated in mutant superoxide dismutase-1 (SOD1) mice that administration of 3K3A-APC after disease onset slows disease progression and extends survival (7). Furthermore, Winkler et al were able to show that blood brain barrier (BBB) breakdown contributes to early motor-neuron degeneration in ALS mice and that restoring BBB integrity via 3K3A-APC during an early disease phase retards the disease process (8).

We propose to use two different doses regimens of 3K3A-APC (15mg and 30mg), similar to doses demonstrated to be safe in stroke patients, in two cohorts of patients with Amyotrophic Lateral Sclerosis. This study will determine safety and tolerability in ALS patients. In addition cerebral [F]FEMPA PET imaging will determine whether microglial activation can be modulated from prior to the infusion (Day 2) to after completion of the infusion (Day 9). An MRI method recently developed by the team at Macquarie University will also be used to assess diffusion kurtosis and integrity of the blood brain barrier (9). Other biomarkers of microglial/monocyte activation will be assayed including kynurenine metabolites in plasma, serum and urine, monocyte activation state in peripheral blood via flow cytometry and proteomics including cytokine and chemokine assays, neurofilaments assays and measurement of soluble CD14.

If microglial activation can be attenuated in ALS, then the progression of ALS might be slowed. While this is an acute dosing study over a short period, the information derived from this study will inform chronic long-term dosing trials for patients with ALS.

## 2. Study Design

ZZ-3K3A-APC-202 is a phase II, single centre, open label, uncontrolled cohort trial of 15mg (initial cohort) and 30mg of 3K3A-APC given twice daily intravenously for a maximum of 5 doses to patients with ALS. Each patient will be admitted to hospital for dosing. For each patient, the trial will run for two weeks, including a ten-day hospital stay for 3K3A-APC IV administration and study evaluations. The study has an estimated completion time of three months. A maximum of 8 patients will participate in each cohort.

### 3. Study Objectives

#### 3.1 Primary Objective

The primary study outcome is the safety of patients with clinically definite ALS administered given up to 5 doses of either 15mg or 30mg of 3K3A-APC 12 hourly. Safety will be evaluated by clinical laboratory testing, physical examination and the collection of adverse events.

In addition, this study aims to determine which dose of 3K3A-APC treatment is able to attenuate microglial activation in the motor cortex of patients with amyotrophic lateral sclerosis, utilizing [F]FEMPA PET imaging prior to, and after treatment. In addition, the study will determine the dose of 3K3A-APC that is most effective in reducing microglial activation.

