#### 3.2 Secondary Objectives

The secondary outcomes are the comparison between the changes in the mean of clinical, imaging and biomic outcomes in various subsets between the two groups. The secondary outcome instruments are:

MRI scan of the brain (Day 2 and Day 9), to determine whether the blood brain barrier integrity can be measured in ALS by Magnetic Resonance Imaging, and whether 3K3A-APC is able to repair it. In addition novel methods of measuring diffusion kurtosis, a marker of neuronal injury will be used.

Extensive biomic measurements of serum, plasma, urine and CSF will be performed. These will include a novel method to determine whether monocyte activation in the peripheral blood can act as a surrogate marker of microglial activation state in ALS. In addition multiplex cytokine and chemokine assays will determine the biological impact of the therapy. Neurofilament, soluble CD14 and kynurenine (and other) measurements will be used to look at acute changes as a result of 3K3A-APC. These methods will determine whether 3K3A-APC therapy is able to attenuate the altered cytokine and metabolic profiles in ALS.

It is highly unlikely that such an acute dosing regimen will identify neurological changes in the subjects, but accurate clinical and biophysical measurements will be performed to detect any such change should they occur.

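### The objectives promise to determine the most effective dose on PET, but the analysis plan gives no between-dose difference, and with at most 8 patients per sequential cohort that difference would be known to about ±1.07 SD of change at best

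*Combined protocol and SAP*

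**What the plan says.** Section 3.1 states that "the study will determine the dose of 3K3A-APC that is most effective in reducing microglial activation". The synopsis, under Primary Outcome, gives the same purpose for having two cohorts: "to determine the dose of 3K3A-APC that is shown to be most effective in reducing microglial activation". Section 3.1 also asks a separate question: which dose is able to attenuate activation, judged by PET before and after treatment.

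The secondary outcome in the synopsis is "Comparison between the changes in the mean of clinical, imaging and biomic outcomes in various subsets between the two dose cohorts". Section 3.2 has nearly the same words: "comparison between the changes in the mean of clinical, imaging and biomic outcomes in various subsets between the two groups". The instruments listed beneath it are MRI and biomic measures; PET is not among them.

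On design, the synopsis specifies cohorts in sequence, "with the initial cohort to receive 15mg and the subsequent cohort to receive 30mg", and Section 2 adds: "A maximum of 8 patients will participate in each cohort". Section 2 calls the trial open label and uncontrolled. Section 13.5 mentions a randomisation date in passing, but no randomisation is described anywhere.

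On analysis, the synopsis statistical methods and Section 15.1 are descriptive: "Data will be summarised by dose cohort, and overall". Section 15.2 summarises the PET result by cohort and overall as observed value, change and % change, with two-sided 95% CIs. Section 15.3 treats MRI and biomic measures the same way. Neither section specifies a between-dose difference, an interval for it, or a criterion for calling one dose most effective.

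**The concern.** Two statements in the objectives call for a contrast between doses: the ranking of doses on PET, and the secondary comparison of mean changes. The analysis sections produce neither. Section 4 says the results will guide dosing for chronic studies, so the dose statement is one that later work will use.

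Followed exactly, the plan leaves that statement to be read off two separate cohort summaries. Two things can go wrong. First, change and % change can rank the doses differently if the cohorts differ at baseline. The plan reports both without saying which one decides, and Section 7.2.2 describes the scan without naming an outcome measure. Second, readers who are shown two separate intervals tend to ask which one excludes zero. That is not a comparison of doses, and it often separates doses that are equal.

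**Working it through.** The documents give no sample-size calculation, effect size, SD of PET change or precision target, so there is no planned figure to reproduce. Results are therefore in units of the SD of individual change from Day 2 to Day 9.

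**Inputs.** Cohort size n = 8 at most (Section 2); 7 and 6 are shown as assumed losses of evaluable scan pairs. Two-sided 95% interval (Section 15.2). Assumed: normal changes, the same SD in both cohorts, and cohorts comparable apart from dose.

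**1. Precision of the between-dose difference.** Half-width = t(0.975, 2n−2) × √(2/n).

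| n per cohort | t | √(2/n) | Half-width (SD) |
|---|---|---|---|
| 8 | 2.145 | 0.500 | 1.07 |
| 7 | 2.179 | 0.535 | 1.16 |
| 6 | 2.228 | 0.577 | 1.29 |

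For comparison, the interval the plan does provide, for one cohort of 8, has half-width 2.365/√8 = 0.84 SD.

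**2. What a simple ranking would achieve.** If the dose with the larger observed mean reduction is picked, the chance of picking the truly better dose is Φ(d√(n/2)), where d is the true difference in SD. With n = 8, √(n/2) = 2.
- d = 0.5: Φ(1.0) = 84%.
- d = 1.0: Φ(2.0) = 98%.

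If the doses are equal, the rule still names a winner every time, and the observed gap is at least 0.5 SD in one direction or the other with probability 2 × (1 − Φ(1)) = 32%.

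**3. Sensitivity to cohort imbalance.** The cohorts are sequential, so take an assumed imbalance of 0.25 SD, with d = 0.5 and n = 8.
- Against the better dose: Φ(2 × 0.25) = 69%.
- In its favour: Φ(2 × 0.75) = 93%.

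The 84% therefore moves to between 69% and 93% under an imbalance of that size. The documents give no basis for choosing the direction.

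**4. Reading the two cohort intervals separately.** Suppose both doses have the same true change. Let p be the chance that a cohort of 8 has a 95% CI excluding zero (one-sample t, 7 df). Exactly one of the two intervals excludes zero with probability 2p(1−p).

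| True change in both cohorts (SD) | p | Exactly one excludes zero |
|---|---|---|
| 0.5 | 0.232 | 36% |
| 0.75 | 0.449 | 49% |
| 1.0 | 0.681 | 43% |

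Equal doses would thus look like one that works and one that does not in roughly a third to a half of such trials.

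**The case against.** The strongest reply is that this is a descriptive pilot and says so: one synopsis aim is "To use the data from this pilot study to inform a larger study". Section 4 promises means and variability in the two cohorts, and Section 15 delivers them. Ranking two doses needs only two means, and the 84% and 98% above show that such a ranking is not worthless. An unadjusted difference and its interval can be rebuilt from the planned n, mean and SD. Most of this stands. No hypothesis test is called for, and a power calculation would be beside the point. What remains is that a difference with its CI is itself descriptive, and it is the summary that the dose-ranking sentence needs.

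Three stronger readings are tempting, and the documents do not support them.
- That Section 15 leaves the PET objectives unanswered altogether. It does not: the question in Section 3.1 about attenuation is within-cohort, and the planned change-from-baseline intervals address it.
- That the PET measure will be picked after the data are seen. The documents show only that it could be. Section 7.2.2 refers to established protocols, Section 12.4 to a companion protocol and Section 13.1 to operation manuals, so the measure may be fixed in material not available here. Section 15.2 also commits to reporting both change and % change, so neither can be dropped.
- That the secondary comparison already covers PET. Its instrument list does not include PET, so it cannot be relied on to fill the gap.

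**Conclusion.** The mismatch holds and is worth fixing, but it is limited to the dose-ranking wording and the missing between-cohort summaries. The planned analysis answers the within-cohort question. It does not supply the between-dose difference or its precision, and it does not say which scale decides.

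The ±1.07 SD half-width is a best case: 8 is a maximum, and any missing Day 2 or Day 9 scan widens it. It rests on normality, a common SD and comparable cohorts. The last cannot be checked from the documents, because dose and calendar time are confounded. With that precision the study can estimate a difference and may favour one dose, but choosing the larger mean would not show that the doses differ.

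A reader might infer that the trial cannot inform dose choice at all, or needs more patients. Neither follows for a pilot. The primary safety analysis is untouched.

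**What to change.** 1. **Section 15.2.** Add one contrast, labelled exploratory and non-randomised: the 30 mg minus 15 mg difference in mean Day 2 to Day 9 change in motor-cortex [18F]FEMPA signal, with a two-sided 95% CI. Fix the PET measure and the scale (change or % change) before any Day 9 data are reviewed, or cite the document where they are already fixed. List TSPO binding affinity, already collected under Section 7.2.1, by cohort beside the contrast, so that a difference in affinity mix is visible.

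2. **Section 3.1 and the synopsis.** Replace the aim of determining the most effective dose with estimating the difference between doses. State the expected precision (about ±1.07 SD of change with 8 per cohort). Say that doses are compared by this difference and not by which cohort's own interval excludes zero. Keep the within-cohort objective as it is.

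3. **Section 15.3.** Report the same descriptive between-cohort difference with its CI for the secondary outcomes that Section 3.2 and the synopsis say will be compared. Alternatively, reword those two places to by-cohort summaries.

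The cost is a less ambitious stated objective, an early commitment to one PET measure and scale, and a few more table rows. No patients, visits or procedures are added.
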